PPSI	Palmoplantar Pustulosis Severity Index
PRO	Patient-report Outcome
Q	Quantile
QoL	Quality of Life
SAP	statistical analysis plan
SAPHO	synovitis, acne, pustulosis, hyperostosis osteitis syndrome
SD	standard deviation
SE	standard error
TEAE	treatment-emergent adverse event
TFLSD	table, figure, and listing shell document
ULN	upper limit of normal
VAS	visual analogue scale

1. Introduction

The purpose of this Statistical Analysis Plan (SAP) is to provide details of the statistical analyses that have been outlined within the protocol for the phase 3 study 20200195 of Apremilast in Japanese subjects with palmoplantar pustulosis (PPP) dated 30 March 2022. The scope of this plan includes the primary analysis (Week 16), supplemental analysis (Week 24), and the final analysis that are planned and will be executed by the Amgen Global Biostatistical Science department unless otherwise specified.

2. Objectives, Endpoints and Hypotheses

2.1 Objectives and Endpoints/Estimands

Objec	tives	Endpoints			
Prima	Primary				
•	To evaluate the efficacy of apremilast 30 mg twice daily (BID) compared with placebo in subjects with PPP	 Achieving at least 50% reduction from baseline in Palmoplantar Pustulosis Area and Severity Index (PPPASI) total score (PPPASI-50) at week 16 			
Seco	ndary				
•	To evaluate the efficacy of apremilast 30 mg BID compared with placebo in subjects with PPP	 Change from baseline in PPPASI total score at week 16 Change from baseline in Palmoplantar Pustulosis Severity Index (PPSI) total score at week 16 Change from baseline in subject's Visual Analogue Scale (VAS) assessment for PPP symptoms (pruritus and pain/discomfort) at week 16 Change from Baseline in Dermatology Life Quality Index 			
		(DLQI) total score at week 16			
•	To evaluate the safety and tolerability of apremilast 30 mg BID compared with placebo in subjects with PPP	 Treatment-emergent adverse events (TEAEs), serious TEAEs, and TEAEs of interest Clinically significant changes in body weight, vital signs, and laboratory abnormalities 			

Primary Estimand

The main estimand of primary interest for the primary efficacy endpoint (i.e., achievement of PPPASI-50 response defined as at least 50% reduction from baseline in PPPASI total score, at week 16) is defined in terms of the following attributes:

- The target population of interest is Japanese subjects with PPP defined through the inclusion/exclusion criteria.
- The primary endpoint is the achievement of PPPASI-50 response at week 16.
- Intercurrent events (IEs) are investigational product (IP) discontinuation due to lack of efficacy, adverse event, or protocol-prohibited medication use. A subject will be considered a treatment failure after any of the IEs.
- The summary measure is the difference between apremilast 30 mg BID group and placebo group in proportion of responders based on the intent-to-treat (ITT) population including all randomized subjects.

A missing value after any of the IEs will be imputed as non-responders, otherwise, will be imputed with a multiple imputation (MI) method. A non-missing value after any of the IEs will also be imputed as non-responders.

Secondary Estimand(s)

The estimands for the secondary efficacy endpoints (i.e., change from baseline at week 16 in PPPASI total score, PPSI total score, subject's VAS assessment for PPP symptoms [pruritus and pain/discomfort], and DLQI total score) are defined in terms of the following attributes:

- The target population of interest is Japanese subjects with PPP defined through the inclusion/exclusion criteria.
- The secondary endpoints are the change from baseline at week 16 in PPPASI total score, PPSI total score, subject's VAS assessment for PPP symptoms (pruritus and pain/discomfort), and DLQI total score.
- The IEs are IP discontinuation due to lack of efficacy, adverse event, or use of protocol prohibited medication. A subject will be considered a treatment failure after any of the IEs.
- The summary measure is the mean difference in change from baseline between apremilast 30 mg BID group and placebo group based on the ITT population.

A missing value after any of the IEs will be imputed using baseline value. Other missing values will not be imputed. A non-missing value after any of the IEs will also be imputed using baseline value.

Exploratory

Exploratory	
່ ງງ	Hunotheses and/or Estimations

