The sample size estimation is based on the results of the phase 2 study (CC-10004-PPP-001 [20200055]). Assuming that a proportion of subjects achieve PPPASI-50 response of 40% and 65% at week 16 for the placebo group and the apremilast 30 mg BID group, respectively, a sample size of approximately 170 subjects in total (85 subjects per group) provides 90% power using a chi-square test with a 2-sided alpha of 0.05. A dropout rate of 5% is anticipated during the double-blind placebo-controlled period of the study.

Planned Analyses

The primary analysis will be performed after all subjects have completed the week 16 visit (visit 8) or have been discontinued from the study. An additional analysis will be conducted after all subjects have completed the week 24 visit (visit 10) or have been discontinued from the study. At the end of the study, after all subjects have either completed the study or been discontinued, the final analysis will be performed. The efficacy analyses will be performed on the ITT population.

The primary endpoint is the achievement of PPPASI-50 at week 16. Subjects who discontinued treatment prior to week 16 (due to lack of efficacy, an adverse event, or protocol deviation due to prohibited medication usage) will be considered as treatment failures and non-responders in the primary analysis. Missing values of the data in which the treatment failures are considered as non-responders will be imputed using multiple imputation (MI).

The treatment difference between the apremilast 30 mg BID group and the placebo group will be analyzed using the Cochran–Mantel–Haenszel (CMH) test, adjusting for the stratification factor at randomization. The 2-sided p-value from the CMH test, the adjusted treatment difference in proportion using the weighted average of the treatment

Protocol Number: 20200195

Date: 15 April 2022 Page 14 of 99

differences across the strata, and the associated 2-sided 95% CI will be provided. The statistical test will be 2-sided at the significance level of alpha = 0.05.

Secondary efficacy endpoints, such as the PPPASI total score change from baseline at week 16, will be analyzed using the mixed-effect model for repeated measures (MMRM) with treatment group, visit time, treatment-by-time interaction, and stratification factors as fixed effects, and the baseline value as a covariate.

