6.1.4 Excluded Treatments and/or Procedures During Study Period

Table 6-2. Excluded Treatments and/or Procedures During Study Period

Prohibited Treatment	Time Period for Exclusion
Strong cytochrome P450 3A4 (CYP3A4) enzyme inducers (eg, rifampin, phenobarbital, carbamazepine, phenytoin and St. John's Wort)	2 weeks or 5 times the half-life, whichever duration is longer, prior to randomization and until the end of active treatment
Granulocyte and monocyte adsorption apheresis	2 weeks prior to randomization until the end of active treatment
Topical therapies that could affect PPP or the efficacy evaluation (including, but not limited to, corticosteroids, retinoid, vitamin D3 derivatives, tacrolimus, antihistamine, antibiotics or traditional Chinese/Japanese herbal preparations).	2 weeks prior to randomization and during double-blind, placebo-controlled period; allowed after week 16 Note: Only use of topical antibiotics for the treatment after skin biopsy is permitted. Unmedicated skin moisturizer (eg, Vaseline) will be permitted as needed.
Conventional systemic therapies that could affect PPP or the efficacy evaluation (including, but not limited to corticosteroids, antihistamine, antibiotics, JAK inhibitors, 1,25-dihydroxy vitamin D3 and analogues, psoralens, sulfasalazine, hydroxyurea, dimethyl fumarate, biotin, or colchicine)	4 weeks prior to randomization until end of active treatment Note: Systemic antihistamines are allowed after week 16
Systemic therapy for PAO including, but not limited to bisphosphonates,	4 weeks prior to randomization and until end of active drug treatment period

Protocol Number: 20200195

Date: 15 April 2022 Page 36 of 99

immunosuppressants [eg, MTX, azathioprine, cyclosporine or 6-thioguanine, mercaptopurine, mycophenolate mofetil, tacrolimus]) and other biologics (eg, anti-IL1 antibody)

Note: Background stable doses of NSAIDs for treatment of PAO are permitted.

Page 1 of 2

Protocol Number: 20200195

Date: 15 April 2022 Page 37 of 99

Table 6-2. Excluded Treatments and/or Procedures During Study Period

Prohibited Treatment	Time Period of Exclusion	
Prolonged sun exposure or used tanning booths or other ultraviolet light sources	4 weeks prior to randomization and until the end of active treatment period	
Biologic therapy such as:		

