TNFα or IL17 blockers (eg, adalimumab, brodalumab, certolizumab pegol, etanercept, golimumab, infliximab, ixekizumab, secukinumab, or biosimilars for each)	12 weeks or 5 times the half-life, whichever duration is longer, prior to randomization and until end of active treatment period. 24 weeks OR 5 times the half-life, whichever duration is longer, prior to randomization and until end of active treatment period.	
Anti-IL12 or anti-IL23 monoclonal antibodies such as guselkumab, ustekinumab or tildrakizumab and other biologics		
Phototherapy (ultraviolet B radiation [UVB] or psoralen ultraviolet A radiation [UVA])	4 weeks prior to randomization; allowed after week 16 during drug treatment period	
The following focal infection treatments for PPP (but not limited to):	24 weeks prior to baseline until the end of active treatment period	
Tonsillectomy for tonsils	Note: Dental therapy (non-invasive dental care [eg, scaling and root planning for	
Endodontic treatment for periapical pathosis	periodontal disease]) is permitted	
Periodontal surgery for moderate to severe periodontitis	throughout the study	
Systemic retinoids (eg, etretinate)	2 years prior to randomization for females of childbearing potential, 4 weeks prior to randomization for females of non-childbearing potential, and 6 months prior to randomization for males until end of active treatment period.	

Page 2 of 2

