9.4.4 Prior and Concomitant Procedures

Prior procedures are defined as those started before Study Day 1 (whether or not ended before Study Day 1). Concomitant procedures are defined as procedures that were either initiated before Study Day 1 and continued during the study treatment, or initiated on/after the date of Study Day 1 and on/before the date of treatment discontinuation. Procedures initiated prior to the start of study treatment and were continued after the start of study treatment will be counted as both prior and concomitant procedures.

Frequency summaries of prior and concomitant procedures will be provided by verbatim term, and location.

A subject listing of prior and concomitant procedures will be provided.

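### As worded, the third intercurrent event covers prohibited medication only, so an IP stop recorded as due to a prohibited non-drug PPP therapy is not a treatment failure

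*SAP*

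**What the plan says.** SAP 2.1 defines the primary estimand's events thus: "Intercurrent events (IEs) are investigational product (IP) discontinuation due to lack of efficacy, adverse event, or protocol-prohibited medication use". SAP 9.5.1 repeats this for the primary analysis, and SAP 2.1 and 9.5.2 repeat it for the secondary endpoints. Protocol 1.1, 3 and 9.4.2.2 have the same restriction. The planned-analyses text of the protocol synopsis puts it as "protocol deviation due to prohibited medication usage".

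The prohibited list is in protocol 6.1.4, Table 6-2, headed "Excluded Treatments and/or Procedures During Study Period". Among its entries are:

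- "Granulocyte and monocyte adsorption apheresis"
- "Phototherapy (ultraviolet B radiation [UVB] or psoralen ultraviolet A radiation [UVA", with the period "4 weeks prior to randomization; allowed after week 16 during drug treatment period"
- focal-infection treatments for PPP, among them "Tonsillectomy for tonsils", endodontic treatment and periodontal surgery

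Under SAP 2.1, 8.3.2 and 9.5.1, every PPPASI-50 value after an intercurrent event becomes a non-response, whether observed or missing. Without an event, observed values stand and missing ones go to multiple imputation (MI). For the secondary endpoints (SAP 9.5.2), values after an event are replaced by baseline. Without an event they are used as observed or left missing for the MMRM.

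**The concern.** The estimand is meant to deny a subject a response once IP has been stopped because another therapy was used. The wording applies that principle to drugs and, read literally, omits non-drug therapies that the protocol itself regards as acting on PPP. Its rationale and background call phototherapy a common PPP treatment, and Table 6-2 describes tonsillectomy and the dental procedures as treatments for PPP. A subject stopped for a topical steroid is a failure. A subject stopped for UVB, with the reason entered as a protocol deviation, is not.

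The same wording drives the primary endpoint and all five secondary endpoints in the testing sequence. If it is left open, someone must decide case by case whether a procedure counts as medication, possibly after unblinding.

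**Working it through.** **Step 1: scope of the two texts.**

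| Table 6-2 entry | Barred in weeks 0-16 | Covered by the word medication? |
|---|---|---|
| Topical, systemic and biologic drugs | Yes | Yes |
| Apheresis | Yes | Not literally |
| UVB phototherapy | Yes (allowed after week 16) | Not literally |
| Tonsillectomy, endodontic treatment, periodontal surgery | Yes | Not literally |
| Prolonged sun exposure, tanning | Yes | No; a lifestyle item |

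Psoralen UVA is a mixed case, because psoralens are also listed among the systemic drugs. The SAP treats procedures and medications under separate headings (9.4.4 and 9.4.5). Section 9.4.4 gives procedures their own definition: "Concomitant procedures are defined as procedures that were either initiated before Study Day 1 and continued during the study treatment", or started on treatment. No section says that prohibited medication means everything in Table 6-2.

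**Step 2: which subjects fall in the gap.** Protocol 7.1 lists the reasons for stopping IP. Lack of efficacy and adverse event are already intercurrent events. The gap is a stop caused by a prohibited procedure and recorded under another reason, such as protocol deviation. Use of a procedure while IP continues is a separate matter and is not counted here.

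**Step 3: what happens to their week-16 PPPASI.** SAP 5.5 ends the placebo-controlled period on the day of discontinuation. The visible windows in SAP Appendix B open week 16 at day 100 (day 86 for DLQI). The available text shows no PPPASI window. Assuming day 100 applies:

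- stop before about day 100: week 16 is missing, so MI; response is possible
- stop from day 100 on: an in-period value counts as observed

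**Step 4: size.** Inputs from SAP 3.2 are 85 per arm, 40% versus 65%, and two-sided alpha 0.05.

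The plan's power reproduces. The pooled rate is 0.525. The null SE is √(2 × 0.525 × 0.475/85) = 0.0766. The alternative SE is √((0.40 × 0.60 + 0.65 × 0.35)/85) = 0.0742. Power = Φ((0.25 − 1.96 × 0.0766)/0.0742) ≈ 0.911, against 90% stated. The point does not affect the sample size.

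One subject changed from responder to failure moves an arm by 1/85 = 1.18 points. If MI credited the planning rate, the expected shift per subject would be 0.40/85 = 0.47 points (placebo) or 0.65/85 = 0.76 points (apremilast). These are rough, because SAP 9.5.1 imputes from treatment, stratum and earlier visits.

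The documents give no count. Assume 0 to 4 per arm, all otherwise responders. Four is about the whole anticipated 5% dropout (0.05 × 85 = 4.25), so it is a ceiling. Start from 34/85 versus 55/85 (unadjusted chi-square):

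| Recoded as failures | Difference (points) | p |
|---|---|---|
| none | 24.7 | 0.0013 |
| 1 / 2 / 4 on placebo only | 25.9 / 27.1 / 29.4 | 0.0007 / 0.0004 / 0.0001 |
| 1 / 2 / 4 on apremilast only | 23.5 / 22.4 / 20.0 | 0.002 / 0.004 / 0.009 |
| equal numbers in both | 24.7 | about 0.0013 |

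Near the boundary one subject can decide: 47 versus 34 responders gives p = 0.046, and 46 versus 34 gives p = 0.065.

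**The case against.** The strongest reply is that medication is shorthand. Table 6-2 is the only prohibited list, and protocol 6.6.2 uses it to limit medications and treatments together, so a sensible analyst would count every therapy on it. That may be the intent, but no section says so, and a programmer working from the SAP could reasonably leave procedures out.

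Four limits on the point stand:

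- **Other events catch many cases.** A subject sent for UVB because disease persists fits lack of efficacy. Protocol 11.4 makes the condition behind a procedure the adverse event, so a stop for a tonsillitis flare can be recorded that way. A reader might infer that every procedure-related stop escapes; the documents do not support that.
- **Few subjects are at risk.** Because focal infection is a stratification factor, a reader might infer that subjects due for such procedures are knowingly enrolled. Exclusions 202 and 203, the exclusion for scheduled surgery and the screening dental examination remove those with a foreseeable need.
- **Early stops mostly reach MI.** A reader might infer that a subject stopped at week 10 is credited with an observed post-phototherapy response. With the period ending at discontinuation and a day-100 window, that value would not be used.
- **Non-responder imputation covers part of it.** That sensitivity analysis (SAP 9.5.1) turns missing non-event values into failures, and a tipping-point analysis is planned. Neither alters an observed value, and SAP Table 9-2 plans no sensitivity analysis for the secondary endpoints.

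**Conclusion.** The point holds on the wording, within narrow limits. An IP stop caused by apheresis, phototherapy or a focal-infection procedure, and recorded as neither lack of efficacy nor adverse event, is literally not a treatment failure, whereas the same stop caused by a drug is. The inconsistency reaches the primary and all five secondary endpoints.

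The effect is probably very small: at most 1.18 points per subject in one arm. Under the assumed ceiling of four in one arm, the difference moves by 4/85 = 4.7 points and significance is kept at the planned rates. A reader might infer a bias towards apremilast, but the documents do not support a direction. If such stops are commoner on placebo, leaving them as possible responders raises the placebo rate and works against apremilast.

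The conclusion assumes that the Appendix B windows apply to PPPASI and that the count is within 0 to 4 per arm. Only the route and size depend on these, not the gap in the definition.

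**What to change.** Before the week-16 database lock, define the third intercurrent event once in SAP 2.1 as IP discontinuation due to use of a prohibited medication, or of a prohibited non-drug PPP treatment or procedure listed in Table 6-2: apheresis, phototherapy, or the listed focal-infection procedures. State that lifestyle items such as sun exposure are not included; citing the whole table without that limit would make a lifestyle lapse an estimand event. Carry the definition into SAP 9.5.1 and 9.5.2, and align protocol 1.1, 3 and 9.4.2.2.

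Identify these stops from the End of IP reason together with the concomitant medication and concomitant procedure records. The Schedule of Activities already collects both at every visit.

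The cost is wording and a short derivation rule. It changes analysis classification only, not patient management. The downside is that responder rates may fall slightly.

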7.1 Discontinuation of Study Treatment

Subjects (or a legally authorized representative) can decline to continue receiving investigational product and/or other protocol-required therapies and/or procedures at any time during the study but continue participation in the study. If this occurs, the investigator is to discuss with the subject the appropriate processes for discontinuation from investigational product or other protocol-required therapies and must discuss with the subject the possibilities for continuation of the Schedule of Activities (see Table 1-1) including different options of follow-up (eg, in person, by phone/mail, through family/friends, in correspondence/communication with other treating physicians, from the review of medical records) and collection of data, including endpoints, adverse events, and must document this decision in the subject's medical records. Subjects who have discontinued investigational product and/or other protocol-required therapies and/or procedures should not be automatically removed from the study. Whenever safe and feasible, it is imperative that subjects remain on-study to ensure safety surveillance and/or collection of outcome data.

Reasons for early removal from protocol-required investigational product(s) or procedural assessments may include any of the following:

- decision by Sponsor
- lost to follow-up
- death
- adverse event
- subject request
- lack of efficacy
- protocol deviation
- pregnancy

Protocol Number: 20200195

Date: 15 April 2022 Page 41 of 99

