9.4.2 Methods of Analyses

9.4.2.1 General Considerations

Efficacy analyses will be performed on the ITT population by randomized treatment group and safety analyses will be performed on the safety population by actual treatment group, unless otherwise specified.

Subject disposition, demographics, baseline characteristics, and exposure to IP will be summarized.

Summary statistics for continuous variables including the number of subjects (n), mean, SD, median, the 25th (Q1) and 75th (Q3) percentiles, minimum, and maximum. All mean and median values will be formatted to 1 more decimal place than the measured value. Standard deviation values will be formatted to 2 more decimal places than the measured value. Minimum and maximum values will be presented to the same number of decimal places as the measured value. Frequency summary for categorical variables includes number of percentages. All percentages will be rounded to 1 decimal place. Number and percentage values will be presented as xx (xx.x%).

Protocol Number: 20200195 Date: 15 April 2022 Page 54 of 99

9.4.2.2 **Efficacy Analyses**

Endpoint/	Statistical Analysis Methods		
Estimand			
Primary	The primary efficacy endpoint is the achievement of PPPASI-50 at		
	week 16 and the main estimand is the difference between apremilast		
	30 mg BID and placebo in proportion of PPPASI-50 responders at		
	week 16 based on the ITT population in which subjects who		
	discontinue IP due to lack of efficacy, adverse event, or use of protocol		
	prohibited medication are considered as treatment failures.		
	The target population of interest is Japanese subjects with PPP defined through the inclusion/exclusion criteria.		
	The primary endpoint is the achievement of PPPASI-50 at week 16.		
	The IEs are IP discontinuation due to lack of efficacy, adverse event, or protocol-prohibited medication use. A subject will be considered as a non-responder after any of the IEs.		
	The summary measure is the difference in proportion of the responders.		
	Missing values of the data in which the treatment failures are		
	considered as non-responders will be imputed using multiple		
	imputation (MI) method based on similar subjects who remained in the		
	study.		
	The treatment difference between apremilast 30 mg BID and placebo		
	will be analyzed using the Cochran–Mantel–Haenszel (CMH) test		
	adjusting for the stratification factor at randomization. The testing will		

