3.2 Sample Size

The primary endpoint is the achievement of PPPASI-50 response at week 16. The sample size estimation is based on the results of the phase 2 study (CC-10004-PPP-001 [20200055]). Assuming a proportion of subjects achieving PPPASI-50 response at week 16 of 40% and 65% for the placebo group and the apremilast 30mg BID group, respectively, a sample size of approximately 170 subjects in total (85 subjects per group) provides 90% power using a chi-square test with a 2-sided alpha of 0.05. A dropout rate of 5% during double-blind placebo-controlled treatment period is anticipated.

4. Covariates and Subgroups

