5.2.5 Study Day

The number of days from Study Day 1, inclusive, given by the following formula:

- Study Day = (Date of interest Date of Study Day 1) + 1, if date of interest is on/after Study Day 1.
- Study Day = (Date of interest Date of Study Day 1), if date of interest is before Study Day 1.

Study Day 1 is defined as the first day of IP administration after randomization. If a subject is randomized but never dosed, then set Study Day 1 to randomization date.

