9.5.1 Analyses of Primary Efficacy Endpoint(s)/Estimand(s)

The primary efficacy endpoint is the achievement of PPPASI-50 response at week 16. The proportion of subjects achieving PPPASI-50 response in apremilast 30 mg BID group and placebo group will be compared using Cochran-Mantel-Haenszel (CMH) test adjusting for the stratification factors for randomization [PPPASI total score range ($\leq 20 / 21-30 / \geq 31$) at baseline and subject's focal infection status (yes/no) at baseline]. The testing will be conducted at the 2-sided 0.05 significance level. Subjects who discontinue IP prior to week 16 due to lack of efficacy, adverse event, or use of protocol prohibited medication will be considered as treatment failures as the result of the IE and the PPPASI-50 values for visits on and after the IE will be imputed as non-responders. The missing data (PPPASI total score) due to other reasons will be imputed using MI method.

The two-sided p-values from the CMH test, the adjusted treatment difference in proportion using the weighted average of the treatment differences across the strata with the CMH weights, along with the associated two-sided 95% CIs using a normal approximation to the weighted average will be provided. Similarly, unadjusted treatment differences in proportions will also be provided.

Sensitivity analyses for the primary endpoint will be conducted using the non-responder imputation (NRI) method for any missing data **due to other reasons (not IE)**. Additionally, to assess sensitivity to departures from the missing data assumption (MAR), the tipping point analysis will be performed. Another sensitivity analysis for the primary endpoint will be performed based on data-derived stratification factors.

For MI method, the SAS procedure MI will be used to impute missing PPPASI scores at the scheduled analysis visits in the Placebo-controlled Phase (Week 0-16) to create M=50 complete datasets. The missing data patterns will be checked at the scheduled

analysis visits, i.e., Baseline (week 0), week, 2, 4, 6, 8, 12, and 16. If there are nonmonotone missing patterns, two separate imputation procedures will be used to complete the imputation process.

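### Death before week 16 is not a named intercurrent event, so whether it counts as non-response or gets an imputed outcome depends on the recorded reason for stopping IP

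*SAP*

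**What the plan says.** **Events that make a subject a failure.** SAP 2.1, primary estimand: "Intercurrent events (IEs) are investigational product (IP) discontinuation due to lack of efficacy, adverse event, or protocol-prohibited medication use". The secondary estimands use the same three reasons, as do Protocol Section 3 and the efficacy table in Protocol 9.4.2.2.

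**Everything else that is missing.** SAP 9.5.1: "The missing data (PPPASI total score) due to other reasons will be imputed using MI method". SAP 8.3.2 and Table 9-1 repeat the rule. Protocol 9.4.2.2 describes the imputation as "based on similar subjects who remained in the" study. For the continuous secondary endpoints, SAP 9.5.2 assigns the baseline value after one of the three events. It leaves all other missing values to the MMRM under missing at random.

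**Death.** Protocol 7.1 opens its list with "Reasons for early removal from protocol-required investigational product(s) or procedural assessments may include any of the following", and death and adverse event are separate entries in it. Protocol 7.2.1 gives death as a reason for removal from the study. SAP Appendix C has rules for completing partial death dates. Neither document says what the week-16 outcome is for a subject who has died.

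**Never dosed.** SAP 5.2.5: "If a subject is randomized but never dosed, then set Study Day 1 to randomization date". This settles a date. No outcome rule goes with it.

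**The concern.** A dead subject has no week-16 skin response. The value does not exist, so it is not missing in the sense that a missing-at-random imputation assumes. Under the stated rule, a death recorded under its own reason goes to the imputation model and may be counted as a responder in some of the 50 completed data sets. The same death recorded as an adverse event is a non-responder in all of them. Two subjects with the same history can thus be scored differently because two sites completed the end-of-IP page differently.

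The rule governs the confirmatory test, and that test opens the fixed sequence of five secondary endpoints. The secondary endpoints share the ambiguity: baseline value in one case, MMRM under missing at random in the other.

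**Working it through.** **Step 1. Follow the rules for a death before week 16.**

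| IP-stop reason recorded | Intercurrent event? | PPPASI-50 at week 16 | Continuous secondary endpoints |
|---|---|---|---|
| Adverse event | Yes | Non-response | Baseline value |
| Death | No | Multiple imputation | Left missing, MMRM |
| Another reason outside the three (for example subject request), death later | No | Multiple imputation | Left missing, MMRM |

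**Step 2. Reproduce the planning figure.** Inputs from SAP 3.2: response of "40% and 65% for the placebo group and the apremilast 30mg BID group", 85 per group; the plan "provides 90% power using a chi-square test with a 2-sided alpha of 0.05". With a pooled rate of 0.525:

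z = (0.25 × √85 − 1.96 × √(2 × 0.525 × 0.475)) / √(0.40 × 0.60 + 0.65 × 0.35) = (2.305 − 1.384) / 0.684 = 1.347

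Power is 91.1%, which agrees with the stated 90%. The sample size is not in dispute; it supplies the rates and the denominator.

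**Step 3. What the imputation credits.** SAP 9.5.1 uses predictive mean matching on treatment, stratification factor and previous visits (K=2, 50 data sets). A subject with only a baseline score should be imputed as a responder at about the arm's own rate. A simulation on assumed score distributions (arm-specific matching, K=2, 50 imputations) gave 65% on apremilast and 40% on placebo. A subject who dies after several visits is imputed from those visits, so the credit can lie anywhere from 0 to 1, with a ceiling of 1/85 = 1.18 points.

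**Step 4. Size, for deaths with no post-baseline score.**

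- One on apremilast: 0.65/85 = 0.76 points added to that arm.
- One on placebo: 0.40/85 = 0.47 points added to that arm.

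With deaths scored as non-response, the difference is 0.65 × (85 − a)/85 − 0.40 × (85 − b)/85, for a deaths on apremilast and b on placebo. With imputation it stays at 25.0 points.

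| a, b | Difference, deaths as non-response | Effect of imputing instead |
|---|---|---|
| 1, 0 | 24.2 points | raises it by 0.8 |
| 1, 1 | 24.7 points | raises it by 0.3 |
| 0, 1 | 25.5 points | lowers it by 0.5 |
| 4, 0 | 21.9 points | raises it by 3.1 |
| 0, 4 | 26.9 points | lowers it by 1.9 |

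The documents give no death rate. The rows with four are outer limits only: they make the whole anticipated 5% dropout in one arm (0.05 × 85, about 4) consist of deaths. Scoring deaths as non-response gives 89.3% power with one death on apremilast only, and 90.4% with one per arm.

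**Step 5. Never-dosed subjects, for comparison.** If the week-16 value is missing, imputation credits an apremilast-arm subject with about 0.65. The plan's own rate without apremilast is 0.40. The excess is 0.65 − 0.40 = 0.25 of a responder, or 0.25/85 = 0.3 points. For a placebo-arm subject it is about zero.

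**The case against.** **A fatal event is already an adverse event.** Protocol Appendix 4 makes a fatal result a criterion for a serious adverse event. The sample contingency form there treats death as an outcome and not as an event term. SAP 9.6.2 tabulates adverse events leading to death. The list in Protocol 7.1 gives possible reasons and is not a coding instruction. A site may well record adverse event, and the subject is then already a failure. This stands, so a reader who infers that every death is imputed goes further than the documents allow. What remains is that neither document says which reason to record, and the outcome turns on it.

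**It is already tested.** The non-responder sensitivity analysis scores such a subject as a non-responder, and a tipping point analysis is planned. Both would show the effect. This limits the consequence, but the primary test still uses the imputed value.

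**Two stronger readings.** A reader might infer that never-dosed subjects should also count as failures, because they cannot discontinue what they never started. The documents do not support a true credit of zero for them. They are alive and have a real week-16 PPPASI, and the plan expects 40% response without apremilast. Protocol 7.1 asks that subjects off IP stay on study for outcome data, so a failure rule could overwrite an observed response. SAP 5.2.5 is a date convention and predicts no number of cases; randomization and first dispensing share Visit 2. Whether to score them as failures is an estimand choice on which statisticians differ.

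A reader might also infer a bias that always favours apremilast. Step 4 shows that the sign depends on the arm in which the deaths fall.

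**Conclusion.** The gap is real and minor. The list of intercurrent events omits death, and the imputation rule then assigns an outcome that does not exist whenever the recorded stop reason is outside the three. With no death rate in the documents, I take 0 or 1 deaths by week 16 as likely. One death with no post-baseline score moves the difference up by about 0.8 points on apremilast or down by about 0.5 on placebo, against 25 planned. These sizes rest on the planning rates, 85 per arm, no post-baseline data and a stop reason not recorded as one of the three. For never-dosed subjects there is only a secondary remark, worth about 0.3 points per apremilast subject whose week-16 value is missing and already covered by the non-responder analysis.

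**What to change.** In SAP 2.1, 8.3.2, 9.5.1, Table 9-1 and 9.5.2, add death from any cause before week 16 as an intercurrent event, whatever IP-stop reason is recorded. Handle it like the other three: PPPASI-50 is non-response from death onward, and the baseline value is assigned for the continuous secondary endpoints. Remove these values from the set to be imputed. Record the difference from Protocol Section 3 and 9.4.2.2 in SAP Section 10.

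Never-dosed subjects need no failure rule. Keep any observed week-16 value.

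The cost is a few lines of SAP text and one programming flag driven by the death date, made before the week-16 database lock. No new data and no change in sample size are needed. Neither arm's response rate can rise under the change, but the treatment difference can move in either direction.
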